We will study older adults (age ≥ 55 yrs.) with mild to moderate AD (n=100) and their caregiver (n=100) randomized (1:1) to one of two intervention delivery strategies for increasing MPA; real-time group video conferencing (RGV) vs. enhanced usual care (EUC). All participants will be provided with an iPad® for intervention delivery, Fitbit for self-monitoring MPA, and will be asked to complete 150 min of MPA/wk. Dyads in the RGV arm will be asked to complete three 45 min sessions that include aerobic, resistance, and balance/coordination exercises delivered by a trained

health coach via Zoom® software on an iPad® during mos. 0-6, and 1 session/wk. during mos. 7-12 to groups of 5-8 dyads in their home. Dyads in the EUC arm, will be given an exercise plan to do own their own. Dyads in both arms will be provided with written materials regarding exercise and physical activity from the National Institute on Aging and will be asked to complete brief (15-20 min) FaceTime™ meetings (0-6 mos.= 2/mo.; 7-12 mos.= 1/mo.) with the health coach to discuss progress, provide support and receive additional guidance on how to increase MPA. Our primary outcome, MPA, will be assessed by accelerometer across the 6 mo. active intervention and total 18 mo. study (secondary outcome).

C. Sample size, statistical methods, and power calculation

We will recruit 100 adults with AD and their caregiver (100 dyads) at baseline to achieve adequate power to test both short-term (0-6 mos.) and long-term (0-18 mos.) effects of the intervention. Our power calculation, based on 21 measurements of MPA, 35 measurements of secondary and exploratory outcomes, a previously observed correlation of 0.22 between repeated measures, and a high attrition rate of ~20%, indicated that this sample size (≥ 42 /arm after attrition) would produce $\geq 80\%$ power to detect an anticipated difference of 10-min/d in MPA ($SD=30$ min/d; $f=0.17$) between adults with AD randomized to RGV and EUC during the active intervention (0-6 mos.). This sample size would also yield $\geq 81\%$ power to test a between-arm difference as small as $f=0.15$, e.g., 6 ± 30 min/d in MPA, during maintenance (7-12 mos.) and no contact (13-18 mos.).

D. Subject Criteria (See Vulnerable Populations appendix, if applicable):

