Schedule. MPA in adults with AD and their caregiver will be assessed at baseline (1 wk. prior to starting the intervention), 3, 6, 12, and 18 mos. Equipment. MPA/sedentary time will be assessed using an ActiGraph model wGT3x-BT tri-axial accelerometer (3.3 x 4.6 x 3.5 cm, wt. = 19 g., dynamic range \pm 8 g). The ActiGraph provides valid and reliable assessments of MPA/sedentary time in adults (70-73). Our group has used the ActiGraph in several trials in a variety of populations including adolescents (74) and adults with IDD (75), and in typically developing children (76, 77) and adults (78, 79). Protocol. There is a lack of consensus on the best protocols to collect, process, and score ActiGraph data (80-82). Thus, our decisions regarding ActiGraph location, monitoring period, data processing etc. were based on current practice, as described below. Participants will be asked to wear the ActiGraph on a belt over the non-dominant hip at the anterior axillary line during waking hours for 7 consecutive days, except for bathing and swimming. A 7-day monitoring period provides a reliable estimate of MPA (81, 83-85). The hip, rather than the wrist location, will be used due to the lack of comparable data and established protocols for assessment of MPA using wrist-worn ActiGraphs (86-88). ActiGraph distribution/reminders. Research staff will distribute and

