Statistical design. Baseline equivalence. The distributional properties of baseline demographic characteristics (MPA, BMI, age, sex, race/ethnicity, etc.) and dyadic relationship between adults with AD and their caregiver (quality, type, number of caregivers) will be inspected within the sample and between the RGV and EUC arms. Variables that demonstrate a significant nonequivalence between RGV and EUC arms will be statistically controlled in the hypothesis testing to improve accuracy of our inferences on intervention effects. Additionally, variables that significantly differ between dyads that dropped out and those that did not will be controlled to minimize any systematic bias stemming from attrition.

Primary aim: *To compare MPA (min/wk.) across the 6-mo. active intervention in adults with AD randomized to RGV and EUC.* Our analysis will account for/evaluate the clustering of observations (repeated measurements; level 1) within participants (level 2) and dyads (level 3; if multiple caregivers) by estimating intra-class correlations and variances/covariances of regression

coefficients at, and across, different levels in random-effects multilevel models (mixed models). To address the aim, models will examine overall between-arm difference in MPV across time (group effect), linear/non-linear change in MPV over time (time effect), and, if appropriate, between-arm difference in this change (group-by-time interaction), while controlling for (i) the number of contacts with research staff and (ii) the baseline characteristics imbalances between participant subgroups (RGV vs. EUC, dropouts vs. completers). For example, a significant interaction would indicate that adults with AD in the RGV arm achieve more minutes of MPA compared to those in the EUC arm and this difference becomes greater as intervention participation increases, i.e., in the later mos.

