Secondary aim: To compare adults with AD and their caregivers randomized to RGV or ECU on the following outcomes across 18 mos. *Adults with AD:* MPA (min/wk.), sedentary time (min/wk.), percentage meeting 150 min/wk. goal, functional fitness, activities of daily living (basic/instrumental), quality of life, residential transitions, neuropsychiatric symptoms, and cognitive function. *Caregivers:* MPA (min/wk.), sedentary time (min/wk.), functional fitness, quality of life, and caregiver burden. Similar mixed models will be fitted separately for these outcome variables to examine group effect, time effect, and group-by-time interaction while controlling for the number of contacts with research staff and the baseline characteristics imbalanced between participant subgroups.

Exploratory aim: To evaluate the influence of process variables/participant characteristics on MPA in adults with AD and their caregiver across 18 mos.: age, sex, BMI, attendance (exercise/support sessions), use of recorded sessions, PA self-monitoring, peer interactions during group sessions, caregiver support, type and quality of the dyadic relationship, number of caregivers, and level of dementia. If MPA is not significantly different between RGV and EUC across 18 mos., i.e., no significant group effect or group-by-time interaction, we will combine the two arms and examine associations of the process variables/characteristics with MPA in mixed modeling. However, if a significant between-arm difference in MPA is identified, we will determine whether the process variables/characteristics enhance or attenuate the treatment effects, i.e., moderation, by testing a 2-way interaction with the group effect and/or a 3-way interaction with the group-by-time interaction term. In addition, we will examine how caregiver MPA influences the MPA of adults with AD over the 6-mo. active intervention, 6 mos. maintenance, and 6 mos. no contact. Some variables will be measured only at baseline, some will be summarized across the trial, while others will be assessed at specific time points. Thus, we will carefully design our models to assure the appropriateness of the analysis.

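### The long-term power sentence equates f = 0.15 with 6 ± 30 min/d, but by the plan's own convention 6/30 is f = 0.10 and f = 0.15 is 9 min/d

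*Combined protocol and SAP*

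**What the plan says.** The section headed Sample size, statistical methods, and power calculation sets 100 dyads "to achieve adequate power to test both short-term (0-6 mos.) and long-term (0-18 mos.) effects of the intervention". For months 0-6 it says the sample "would produce $\geq 80\%$ power to detect an anticipated difference", which it gives as an "anticipated difference of 10-min/d in MPA ($SD=30$ min/d; $f=0.17". The next sentence adds that the same sample has at least 81% power for a "between-arm difference as small as $f=0.15$, e.g., 6 ± 30 min/d in MPA", during maintenance (months 7-12) and no contact (months 13-18).

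The stated inputs are at least 42 per arm after about 20% attrition, 21 measurements of MPA, 35 measurements of secondary and exploratory outcomes, and a correlation of 0.22 between repeated measures. Alpha, sidedness and the test are not given with the power statement. No other SD and no other definition of f appears in the document.

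**The concern.** The two sentences stand side by side, use the same SD and give f both times. At a fixed SD, f is proportional to the difference. If 10 min/d is 0.17, then 6 min/d cannot be 0.15.

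This is the only sentence that says what long-term difference the trial can detect, and 100 dyads are justified partly by it. A reader would take 6 min/d (6 × 7 = 42 min/wk) to be detectable with more than 80% power in months 7-18, while the stated f corresponds to 9 min/d (63 min/wk). A null long-term result could then be read as ruling out a 6 min/d effect that the trial had limited power to find.

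**Working it through.** **1. Conversion.** For two equal arms (the plan randomises 1:1), f = (difference/SD)/2.

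- Plan's months 0-6 figure: (10/30)/2 = 0.167, which rounds to the stated 0.17. The convention is confirmed.
- Plan's long-term example: (6/30)/2 = 0.10, not 0.15.
- Inverting f = 0.15 at SD 30: 2 × 0.15 × 30 = 9 min/d.
- Inverting f = 0.15 at 6 min/d: SD = 6/(2 × 0.15) = 20 min/d.
- Reading f as difference/SD gives 6/30 = 0.20, also not 0.15, and would contradict the 0.17.

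This step needs no alpha, test or correlation.

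**2. Size, whichever single-contrast test was used.** 6/9 = 2/3, so equal power needs (3/2)² = 2.25 times the sample. With a noncentral t on 82 df, 81% power needs a noncentrality of 2.872 (two-sided 5%) or 2.544 (one-sided 5%). At two-thirds of those values power is 47% or 51%.

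**3. Specific tests.** Inputs from the plan: SD 30, correlation 0.22, and 80 to 84 analysed (50 per arm less 20% is 40 per arm; the plan says 42). Assumptions: two-sided 5%, equal correlation between all days, 21 measurements read as 3 weeks × 7 days and 35 as 5 weeks × 7 days. The MPA schedule supports that reading, since MPA "will be assessed at baseline (1 wk. prior to starting the intervention), 3, 6, 12, and 18 mos". The weeks at months 12 and 18 then supply 14 days.

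Per-person variance with m days:

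- unadjusted mean: 900(0.78/m + 0.22)
- change from the 7-day baseline: 900(0.78/m + 0.78/7)
- baseline-adjusted: 900(0.78/m + 0.22) − (900 × 0.22)²/[900(0.78/7 + 0.22)]

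The standard error of the arm difference is √(4 × variance/N).

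*Reproducing the primary claim.* Unadjusted, m = 21: variance 900(0.0371 + 0.22) = 231.4. With N = 84 the standard error is 3.32, so 10/3.32 = 3.01 and power is 84.5% (82.7% with N = 80). With only the 14 post-baseline days it is 80-82%. The plan's claim of at least 80% holds.

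*The long-term example.* Unadjusted, m = 35, N = 84: variance 218.1, standard error 3.22, 6/3.22 = 1.86, power 45%. For 9 min/d the same test gives 9/3.22 = 2.79 and 79%.

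Power for 6 min/d, SD 30, two-sided 5%, N = 80 to 84:

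| Test | Power |
|---|---|
| Unadjusted, 35 days (counts the baseline week as treated) | 43-45% |
| Unadjusted, 14 days (months 12 and 18) | 39-41% |
| Change from baseline, 14 days | 58-60% |
| Baseline-adjusted, 14 days | 69-71% |
| One 7-day week only: unadjusted / change / adjusted | 33-35% / 46-48% / 54-56% |
| Baseline-adjusted, all four post-baseline weeks (28 days) | 79-81% |

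Simulation with 20,000 runs agreed within about one percentage point for the settings simulated. Unlimited repeated measures would raise the unadjusted test only to 47-49%, because the correlation of 0.22 sets a floor on the variance.

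*Difference detectable with 81% power* at months 12 and 18: 9.9-10.1 min/d unadjusted, 7.7-7.9 as change, 6.8-6.9 baseline-adjusted.

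**The case against.** The strongest reply is that the power claim attaches to f = 0.15 and that 6 ± 30 is only an illustration. The unadjusted test with 35 measurements and 42 per arm gives 79-80% at f = 0.15 (noncentral F to normal approximation) and 45-46% at f = 0.10, so the 81% sits close to f = 0.15. Changing one digit, 6 to 9, would reconcile the sentence. This stands as the likelier explanation, but the documents do not settle it. An example of an effect said to be as small as f = 0.15 must itself be at least that large, and 6 min/d at SD 30 is not.

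A second reply is that some tests do bring 6 min/d to about 81% or above. That is true:

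- Baseline adjustment over all four post-baseline weeks gives 79-81%, but this is not the months 7-18 comparison the sentence names.
- One-sided 5% with baseline adjustment at months 12 and 18 gives 79-81%.
- With all 100 retained, that adjusted test gives 78% two-sided and 87% one-sided.
- A group-by-time interaction formula at f = 0.10 with 42 per arm gives 83% with 21 time levels and 95% with 35, but 70.5% with 14. It treats every day as a separate level and tests a different effect from an average difference.

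The power section specifies none of these. The analysis section commits to baseline adjustment only conditionally: "Variables that demonstrate a significant nonequivalence between RGV and EUC arms will be statistically controlled in the hypothesis testing". For the secondary outcomes it says "Similar mixed models will be fitted separately for these outcome variables to examine group effect, time effect, and group-by-time interaction", without saying which term carries the long-term claim. So the shortfall in power depends on the test. None of these variants makes 6/30 equal to f = 0.15.

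Finally, the consequence is modest: one sentence about a secondary outcome. That is accepted.

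**Conclusion.** The concern holds. By the plan's own convention, 6 ± 30 min/d is f = 0.10 and f = 0.15 is 9 min/d, a factor of 1.5 in the difference and 2.25 in sample size. This part is certain and rests on no assumption.

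If f = 0.15 is intended, the example is wrong. Whether 81% is then exactly met turns on the unstated alpha, sidedness and test, and no separate error is claimed there. If 6 ± 30 min/d is intended, at least 81% is not met by the unadjusted test that reproduces the primary claim (43-45%), nor by a two-sided baseline-adjusted comparison at months 12 and 18 (69-71%). Those figures assume 5% alpha, equal correlation of 0.22, 80 to 84 analysed and the day counts above.

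The sentence should be corrected because it is the only support for adequate long-term power. The primary claim stands.

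**What to change.** Make f, the difference and the SD agree: f = 0.15 with 9 min/d at SD 30, or 6 min/d at SD 30 with f = 0.10, or state the other SD if one was used. Then restate the long-term power, or the detectable difference, from that calculation. So that the restated figure can be checked, give the test, alpha and sidedness, and say whether baseline MPA is adjusted for and which assessment weeks are counted.

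The cost is rewriting one or two sentences. The stated detectable difference or power may become less favourable. No change to enrolment, design or analysis is needed.

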Primary care physician (PCP) clearance will be required of participants with AD and their caregiver. To enhance generalizability, individuals taking AD or other medications, or receiving treatment for other chronic diseases, or with risk factors such as hypertension, tobacco use, lipid abnormalities, T2DM, etc., will be allowed to participate with PCP clearance. *Inclusion criteria (Adults with AD):* *Inclusion:* 1) Very mild to moderate dementia (MMSE or STMS ≥ 11 ; Telephone Interview for Cognitive Status (TICS) ≥ 6). 2) Age ≥ 55 yrs. 3) Low-risk of falls, assessed by PCP consent 4) Ability to participate in MPA, e.g., walk including with an assistive device, as verified PCP clearance. 5) Ability to communicate verbally. 6) Vision and hearing sufficient to safely comply with the intervention program as verified by PCP clearance. 7) Reside at home and receive support from a caregiver. 8) Internet access in the home. *Exclusion criteria (Adults with AD):* 1) Current exercise, i.e., > 3 , 30-min bouts of planned exercise/wk. 2) Clinically significant psychiatric disorder; systemic illness or infection likely to affect safety; clinically-evident stroke; myocardial infarction or coronary artery disease in the last 2 yrs.; cancer in the last 5 yrs.; or significant pain or musculoskeletal symptoms that would prohibit exercise. 4) Unwilling to be randomized. *Inclusion criteria (caregivers):* 1) Age ≥ 18 yrs. 2) Spends at least 20 hrs./wk. with the adult with AD. *Exclusion criteria (Caregiver):* 1) Unable to participate in MPA, i.e., brisk walking. 2) Unwilling to be randomized. 3) Serious medical risk, such as cancer within the last 5 yrs. or cardiac event, i.e., heart attack, stroke, angioplasty within the last 2 yrs.

E. Specific methods and techniques used throughout the study

Randomization. Cohorts of ~20 dyads will be stratified by sex and computer randomized by the study statistician with equal allocation to the RGV or EUC arms. Intervention assignments will be concealed in envelopes and delivered to the study coordinator. Assignments will be revealed to adult/caregiver dyads at the orientation session described below.

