Health coach training/blinding/fidelity. Training. We currently have 3 health coaches with experience in delivering group exercise using video conferencing to adults with AD. If needed, new health coaches will be trained by Drs. [name] and [name], and will shadow an experienced health coach for a minimum of 3 mos. prior to delivering the intervention on their own. [name] will train health coaches on how to perform each exercise, the order of presentation of the exercises, and provide guidance on how to recognize and correct common mistakes in performing specific exercises. [name] will provide training regarding strategies for effective communication with adults with AD, i.e., speaking clearly and slowly, providing/repeating simple specific instructions (68), focusing on reassurance and empathy for each participant (69), and fostering interaction between participants with strategies to ensure the focus of the interactions is not on dementia (67). Blinding. The nature of this trial precludes blinding of the health coaches; however, investigators, data analysts and research assistants will be blinded to condition. Intervention fidelity. Recordings from all group exercise sessions (RGV only) and individual support sessions will be reviewed. [name] will compare recordings of both group exercise and support sessions with a check list of exercises/topics scheduled to be included in each session. Health educators covering <80% of scheduled content, or failing to deliver physical activity as prescribed, will receive additional training from [name], and will be dismissed if the problem recurs.

ASSESSMENTS

MPA. Primary outcome (Baseline (0 mos.)- 6 mos.)/Secondary outcomes (0-18 mos.)

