demonstrate proper placement of the ActiGraphs at home visits scheduled at 0, 6, 12 and 18 mos. ActiGraphs will be distributed by mail for the 3-mo. assessment. Daily reminders to comply with the ActiGraph protocol will be sent to participant's iPad® each morning during the 7-day monitoring period. We have employed similar distribution and reminder protocols in previous trials (74 , 75-77, 79). Our current supply of ActiGraphs, plus the additional units requested in this proposal, will allow physical activity assessments to be completed on all participants in the proposed timeframe. Data collection. ActiGraphs will be initialized and downloaded using ActiLife Software version 6.13.3 or higher (ActiGraph Corp, Pensacola, FL) and set to collect in the raw data mode from all 3 axes at 60 Hz. Although the wGT3x-BT collects raw data from 3 axes, the widely used cut-points for determining activity intensity in adults proposed for this trial use acceleration data from the ActiGraph vertical axis (89). However, raw data from all 3 axes will be downloaded and stored, and will be available should algorithms for processing this data become available during this trial. Data processing Accelerometer data will be processed using the protocol for adults used in the 2003-2004 and 2005-2006 cycles of NHANES (89, 90). Data will be aggregated over 60-sec epochs. The following intensity cut-points will be used: sedentary (< 1.0 MET; ≤ 100 counts/min), light (1.1-2.99 METs; 101-2019 counts/min.), moderate (3.0-5.99 METs; 2020-5988 counts/min) and vigorous ≥ 6 METs; ≥ 5999 counts/min) (89, 90). Non-wear time will be defined as at least 60 consecutive minutes of zero counts, with allowance for 1-2 min of counts between 0 and 100. Counts ≥ 20,000/min will be considered spurious (91). All accelerometer data processing will be completed using custom SAS-/R programs developed by Drs. [name] and [name], the project statisticians, in collaboration with our research group. Missing accelerometer data. Recent advances in both statistical methods and computing power have made it possible to impute missing data with large data sets, such as will be collected in the proposed trial, i.e., 7 wk.-long assessments across 18 mos. A detailed description of the methods and procedures for handling missing ActiGraph data (non-wear and device malfunction time) is included in the analysis plan. MPA data for both adults with AD and caregivers will be analyzed including and excluding video conference exercise sessions (RGV arm).

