The study statisticians [name] and [name] will review of the rate of subject accrual and adherence to inclusion/exclusion criteria will occur quarterly to assure that participants meet eligibility criteria and ethnic diversity goals outlined in the grant proposal.

Measurement and Reporting of Participant Compliance to the Treatment Protocol.

Compliance to the intervention will be reported monthly by the study statisticians. To monitor compliance, they will report the group attendance at group exercise sessions (RGV) and/or individual health education sessions (EUC). Compliance to the intervention protocol will be reviewed monthly by the MPIs. We are using an intent-to-treat design; thus, participants will not be dismissed for non-compliance, but will be counseled on strategies to improve compliance during scheduled FTF or RD sessions.

Safety Officer. The safety officer for this trial will be [name]. [name] is a Neurologist at the University of Kansas Alzheimer's Disease Center and is not affiliated with the study in any other fashion and is not in the MPI's chain of command. zhe will review the reports sent by the study coordinator semi-annually and adverse events as they occur and will use the checklists attached to this document to determine whether there is any action, such as an ad hoc review or stopping rule violation that should be communicated to the study investigators, The University of Kansas Human Subjects Committee, or NIH. In addition, the safety officer may comment on whether the study investigator needs to report any specific out of range laboratory data to the participant, and/or their physician.

II. Subject Participation

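### The protocol says investigators and data analysts are blinded, but its own randomisation, compliance-reporting and analysis procedures do not deliver that blinding

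*Combined protocol and SAP*

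**What the plan says.** - *Health coach training/blinding/fidelity*: coaches cannot be blinded, but "investigators, data analysts and research assistants will be blinded to condition".
- *Randomization*: cohorts of about 20 dyads, with sex as a stratification factor, are "computer randomized by the study statistician with equal allocation to the RGV or EUC arms". On concealment, the section adds: "Intervention assignments will be concealed in envelopes and delivered to the study coordinator".
- *Measurement and Reporting of Participant Compliance to the Treatment Protocol*: "Compliance to the intervention will be reported monthly by the study statisticians", and to do so "they will report the group attendance at group exercise sessions (RGV) and/or individual health education sessions (EUC"). As to who sees the result, the section says: "Compliance to the intervention protocol will be reviewed monthly by the MPIs".
- *Adverse Event Grading*: the principal investigators decide the severity of each event and its relatedness to the intervention.
- *Data processing*: the accelerometer programs are written by two people described as "the project statisticians, in collaboration with our research group". Under *Missing accelerometer data*, moderate physical activity (MPA) is to be "analyzed including and excluding video conference exercise sessions (RGV arm").
- *Statistical and Data Analysis*: the primary model adjusts for the count of staff contacts and for baseline variables that turn out to be imbalanced. The shape of the time trend, the use of the group-by-time interaction and the auxiliary variables for imputation are left for later decision.

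**The concern.** The blinding statement covers two groups, investigators and data analysts, whose described duties bring them into contact with allocation. A reader of the trial report would take from that statement that decisions about the primary analysis were made without knowledge of arm. If they were not, the choices still open could be made, even unintentionally, by someone who knows which participants had the video sessions. The protection being claimed would then not exist for that stage.

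**Working it through.** The plan gives no figure to reproduce here. The check sets the sections side by side and adds one count.

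**1. Statisticians.** The person who generates the sequence knows it. The envelopes hide assignments from other staff, not from that person. The monthly attendance report names the arms, and the statisticians prepare it. The project statisticians also program the primary outcome.

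**2. Investigators.** They review compliance monthly, and the report behind that review labels attendance by arm. They also judge whether an adverse event is related to the intervention. Events are collected at group exercise sessions among other places, and only the RGV (group video) arm has those, so an event recorded there identifies the arm.

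**3. Safeguards looked for.** No section describes a separate unblinded statistician, coded arm labels, a blinded data review, or a freeze of the analysis before arm data are seen. *Data Collection and Protection* limits statisticians to de-identified data, which removes identity but not arm.

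**4. Would coded labels be enough?** Count scheduled staff contacts in months 0-6. Inputs: 3 group sessions per week in RGV (*RGV arm, Schedule*) and 2 support sessions per month in both arms (*Individual support sessions*). Assumptions: six months is 24 to 26 weeks, and group sessions count as contacts, a term the plan does not define.

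| | RGV | EUC (enhanced usual care) |
|---|---|---|
| Group sessions | 3 × 24 = 72 to 3 × 26 = 78 | 0 |
| Support sessions | 2 × 6 = 12 | 2 × 6 = 12 |
| Scheduled total | 84 to 90 | 12 |
| At pilot attendance (77% group, 87% support) | 0.77 × 72 + 0.87 × 12 = 65.9 to 0.77 × 78 + 0.87 × 12 = 70.5 | 0.87 × 12 = 10.4 |

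An RGV participant who attends no support session at all still passes the EUC scheduled maximum of 12 on reaching 13 group sessions. That is 13/78 = 16.7% to 13/72 = 18.1% attendance. On these assumptions the covariate reveals the arm for nearly everyone. If group sessions were not counted, both arms would be scheduled at 12 and the covariate would say little. The analysis that removes video sessions would still show who had them.

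**5. What remains open to choice.**
- Covariates: the candidate list is open-ended and no significance threshold is given.
- Time: linear or non-linear.
- Interaction: examined only if judged suitable.
- Imputation: the auxiliary variables are not named.

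**The case against.** The strongest reply is that the text never says who fits the final models. It speaks of a study statistician, study statisticians, project statisticians and data analysts, without defining the last. A separate blinded analyst is therefore possible. This stands in part: the documents do not show that the analysts are unblinded, only that the blinding is not achievable as described. No such person or firewall appears, and the planned inputs would unmask one once the data were loaded.

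Other points also stand. The attendance report may be aggregate and contains no MPA, so it gives the investigators no outcome results by arm. MPA is measured by device, home assessments are done by blinded staff and data entry is blinded. Selecting covariates by baseline imbalance treats the two arms symmetrically, so knowing which one is RGV adds little to that step.

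A reader might infer three stronger things, none of which the documents support.
- **That outcome measurement is biased.** Nothing described here touches ascertainment.
- **That the type I error is inflated by a calculable amount because the analyst knows the arm.** Choosing between the group effect and the interaction after seeing results is a pre-specification problem. Two-sided p-values do not change when the arms are relabelled, so masking would not cure it.
- **That the definition of non-wear is open to discretion.** *Data processing* fixes it, along with the epoch length, cut-points and spurious-count limit.

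**Conclusion.** The point holds as an internal inconsistency with a practical consequence. The blinding claimed for investigators and data analysts is not delivered by the procedures in the same document. For the randomising statistician, the text makes blinding impossible. For the principal investigators, it is contradicted at arm level by the attendance review and, for some events, by adverse event review. For whoever fits the models, it is unsupported rather than disproved.

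The exposure is confined to the open analysis choices. The documents give no basis for putting a size on any resulting bias. The finding that coded labels alone would fail rests on group sessions counting as contacts or, failing that, on the analyst receiving the session times needed to exclude video sessions. This should be corrected, but it does not by itself undermine the trial.

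**What to change.** 1. **Split the roles.** The compliance and data-processing sections each refer to two statisticians. One should generate the allocation and prepare the monthly compliance reports. The other should do neither.
2. **Lock before release.** The second statistician finalises and dates the accelerometer code, covariates, time form, primary contrast and imputation model before receiving arm labels, contact counts or session timestamps. The first statistician holds those items until the lock. Because covariates cannot be settled in advance if they depend on observed imbalance, name them or write the selection rule and its threshold into the locked code. Define what counts as a contact at the same time.
3. **Restate the blinding paragraph.** Assessors and data-entry staff are blinded. The analysing statistician is blinded until the lock. The principal investigators, the randomising statistician and the health coaches are not blinded.

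The cost is a division of duties among existing staff, the work of completing and dating the specification early, and a corrected paragraph. The downside is less flexibility in sharing statistical work.
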